7.1.7. Adverse Events

Adverse events (AEs) will be collected and assessed throughout the study according to the Schedule of Visits and Assessments ([Section 2](#)). The Investigator is responsible for ensuring that all adverse events observed by the clinical staff or reported by the Parent/Caregiver that occur after the first application of investigational product through the end of the study are recorded in the subject's medical record and the eCRF.

The Investigator is responsible for ensuring that all serious adverse events observed by the clinical staff or reported by the Parent/Caregiver that occur after signing of the informed consent through 30 days after the last day of the application of the investigational product or the end of study (whichever is later) are recorded in the subject's medical record and are submitted per SAE reporting requirements ([Section 7.7.1](#)).

AEs (whether serious or non-serious) and clinically significant abnormal laboratory test value(s) will be evaluated by the PI and treated and/or followed up for up to 30 days after end of treatment or until the symptoms or value(s) return to normal, or acceptable levels, as judged by the PI. Refer to [Section 7.7](#) for further details on Adverse Events.

7.2. Efficacy Evaluations

For efficacy evaluation subjects will have $\geq 3\%$ BSA of AD involvement (excluding the scalp, palms, soles). Palms and soles may be treated with investigational product in this study, but will not be counted towards vIGA-AD, EASI, or BSA assessments. EASI is evaluated for the entire body except the scalp, palms, and soles.

7.2.1. Validated Investigator Global Assessment Scale for Atopic Dermatitis (vIGA-AD)

Validated Investigator Global Assessment scale for Atopic Dermatitis (vIGA-AD) assessments should be completed prior to other physician assessments.

vIGA-AD assessment will be performed according to the Schedule of Visits and Assessments ([Section 2](#)). The vIGA-AD is a static evaluation of qualitative overall AD severity. This global assessment scale is an ordinal scale with five severity grades (reported only in integers of 0 to 4). Each grade is defined by a distinct and clinically relevant morphologic description that minimizes inter-observer variability (see [Appendix 2](#)). vIGA-AD is evaluated for the entire body except the scalp, palms, and soles.

Note: All atopic dermatitis lesions on a subject will be treated including the face, trunk, genitals/skin folds, or limbs (excluding the scalp). The palms and soles will be treated but will not be counted towards any measurements of efficacy (EASI, vIGA-AD, BSA, SCORAD).

- **Every effort must be made for the same Evaluator to complete the IGA for the subject at every study visit.**
- **IGA will be assessed at clinic visits prior to the Investigational Product application at the site.**

7.2.2. Eczema Area and Severity Index (EASI)

EASI scores ([Hanifin 2001](#)) will be performed according to the Schedule of Visits and Assessments ([Section 2](#)).

Four anatomic sites – head, upper extremities, trunk, and lower extremities – are assessed for erythema, induration/infiltration (papules), excoriation, and lichenification as seen on the day of the examination. The severity of each sign is assessed using a 4-point scale (half steps are allowed; e.g. 0.5, 1.5 and 2.5):

- 0 = none
- 1 = mild
- 2 = moderate

- 3 = severe

The area affected by atopic dermatitis within a given anatomic site is estimated as a percentage of the total area of that anatomic site and assigned a numerical value according to the degree of atopic dermatitis involvement as follows:

- 0 = no involvement
- 1 = 1-9%
- 2 = 10-29%
- 3 = 30-49%
- 4 = 50-69%
- 5 = 70-89%
- 6 = 90-100%

The EASI score is obtained by using the formula below for subjects <8 years old:

$$\text{EASI} = 0.2 (E_h + I_h + E_{xh} + L_h) A_h + 0.2 (E_u + I_u + E_{xu} + L_u) A_u + 0.3 (E_t + I_t + E_{xt} + L_t) A_t + 0.3 (E_l + I_l + E_{xl} + L_l) A_l$$

Where E, I, Ex, L, and A denote erythema, induration, excoriation, lichenification and area, respectively, and h, u, t, and l denote head, upper extremities, trunk, and lower extremities, respectively.

Note: Palms and soles may be treated with investigational product in this study, but will not be counted towards IGA, EASI, SCORAD, or BSA assessments. EASI is evaluated for the entire body except the scalp, palms, and soles.

7.2.3. Worst Itch-Numerical Rating Scale (WI-NRS)

The WI-NRS has been developed as a simple, single item to assess the patient-reported severity of this symptom at its highest intensity during the previous 24-hour period (Newton 2019). The WI-NRS will be determined by the parent/caregiver recording of daily assessment of worst itch over the past 24 hours. The scale is from '0 to 10' ("no itch" to "worst itch imaginable" or "worst imaginable itch").

Date (DD/MMM/YYYY): _____ / _____ / _____			Time (HH:MM): _____ : _____			 AM	 PM			
Please rate your itching severity by circling the number that best describes your worst level of itching in the past 24 hours:										
0	1	2	3	4	5	6	7	8	9	10
0 = No itch				10 = Worst itch imaginable						
Copyright © 2019 Eli Lilly and Company. All rights reserved.										

WI-NRS Assessments will be performed according to the Schedule of Visits and Assessments ([Section 2](#)) starting 7 days prior to the Baseline/Day 1 clinic visit (during the 7 days prior to Baseline/Day 1, the parent/caregiver will record the WI-NRS value every day).

Parents/guardians will be reminded not to review responses from the previous days when completing the WI-NRS. Parent and/or guardian will be trained at the screening visit in the accurate completion of the WI-NRS.

7.2.4. Children's Dermatology Life Quality Index (CDLQI)

CDLQI will be performed according to the Schedule of Visits and Assessments ([Section 2](#)). The Children's Dermatology Life Quality Index (CDLQI; ≥ 4 years old) allows a simple, compact and uniform assessment of patients with skin diseases in general, in which higher scores indicate poorer disease-related quality of life. Parents/caregivers will complete the CDLQI.

See [Appendix 3](#) for the CDLQI.

7.2.5. Infants' Dermatitis Quality of Life Index (IDQOL)

IDQOL will be performed according to the Schedule of Visits and Assessments ([Section 2](#)). The Infants' Dermatitis Quality of Life Index questionnaire ([Appendix 4](#)) is designed to assess the impact of atopic dermatitis on the quality of life of infants below the age of four years.

It is self-explanatory and should be completed by the child's parent(s) or regular caregiver.

7.2.6. Dermatitis Family Impact Questionnaire (DFI)

This questionnaire measures how much having a child with atopic dermatitis affects the quality of life of other (adult) members of the family. To be completed by parents/guardians/caregivers of subjects ([Appendix 5](#)).

7.2.7. Medical Photography

Photography of AD lesion(s) selected by the Investigator will be performed by all sites at all investigational visits, except Week 2/Day 15. All efforts will be made to de-identify the subjects. Canfield equipment will be used to capture photographs.

Photography should be focused on single lesions or specific body sections (e.g., arm). Body or half body photos should only be taken if necessary. Subjects who are unwilling to participate in the medical photography will be allowed to opt out of this procedure and documented on the informed consent.

Refer to the current Photography Manual for instructions regarding photography.

7.3. Other Evaluations

7.3.1. Body Surface Area (BSA)

BSA assessments will be performed according to the Schedule of Visits and Assessments ([Section 2](#)).

The BSA affected for atopic dermatitis will be determined by the subject's hand method, where the subject's hand (including fingers) surface area is assumed to equal 1% of body surface area (excluding the scalp, palms, soles).

7.3.2. SCORAD ("SCORing Atopic Dermatitis")

SCORAD is a clinical tool for assessing the severity (i.e. extent, intensity) of atopic dermatitis as objectively as possible. It gives approximate weights of 60% to intensity and 20% each to spread (extent) and subjective signs (pruritus and insomnia, etc.). See [Appendix 6](#).

7.3.3. Patient-Oriented Eczema Measure (POEM)

The Patient-Oriented Eczema Measure (POEM) is a tool used for monitoring atopic eczema severity. It focuses on the illness as experienced by the patient.

POEM is a 5-point scale measuring the frequency of each of seven AD symptoms (dryness, itching, flaking, cracking, sleep loss, bleeding, and weeping) over the past week scored as occurring “no days” (0), “1 to 2 days” (1), “3 to 4 days” (2), “5 to 6 days” (3) or “every day” (4). Total score ranges from 0–28, with higher score indicating greater symptom impact.

See [Appendix 7](#). The self/proxy report questionnaire will be used in this study (for children unable to read and/or understand the POEM questionnaire, the parent/guardian/caregiver will complete the questionnaire).

7.4. Final Study Visit – End of Study

The approximate final study visit will occur at Week 4/Day 29. The procedures performed during this visit are as described in the Schedule of Visits and Assessments ([Section 2](#)). A 3-day scheduling window is allowed for this visit. Adverse events will be recorded as reported by the participant or followed to resolution or stabilization (as necessary).

7.5. Early Termination Visit

If a subject is withdrawn or wishes to exit the study, a termination visit will be scheduled. This visit should include the procedures and assessments that would be performed at the Week 4/Day 29 visit.

7.6. Unscheduled Visit

Unscheduled visits may be necessary to repeat testing following abnormal laboratory results, for follow-up of AEs, or for any other reason, as warranted in the judgement of the Investigator.

The following information will be collected for all subjects:

- Concomitant medications/procedures
- AEs

The following information also will be collected:

- vIGA-AD and EASI
- BSA affected with AD
- Local tolerability assessment (by Investigator)

However, if an unscheduled visit is required for reasons other than safety (e.g. procedures such as labs or images that were either missed at the regular subject visit or need to be repeated), the vIGA-AD and EASI, BSA affected with AD, and Local Tolerability assessment (by Investigator) are not required.

The rules for how to tally vIGA-AD, BSA or other proportions of categorical responses will be described in the Statistical Analysis Plan.

7.7. Adverse Events

7.7.1. Adverse Event Definition

An AE is defined as any untoward medical occurrence associated with the use of a drug in humans, whether or not considered drug related. An AE can therefore be any unfavorable and unintended sign (including an abnormal laboratory finding), symptom, or disease temporally associated with the use of a medicinal (investigational) product, whether or not related to the medicinal (investigational) product.

A treatment emergent adverse event (TEAE) is defined as an AE that started post application of study medication at the Baseline visit or was present at treatment initiation but worsened during treatment, through study completion.

The definition of AEs includes worsening of a pre-existing medical condition. Worsening indicates that the pre-existing medical condition has increased in severity, frequency, and/or duration or has an association with a worse outcome. When recording such events, provide descriptions that the pre-existing condition has changed (e.g., worsening hypertension for a subject with pre-existing hypertension). A pre-existing condition that has not worsened during the study or involves an intervention, such as elective cosmetic surgery or a medical procedure while on study, is not considered an AE.

Progression of treatment atopic dermatitis including new or worsening of anticipated clinical signs or symptoms, which are collected as clinical efficacy variables and assessed as unequivocally associated with the disease progression and /or lack of efficacy, should NOT be reported as adverse events unless the disease progression is greater than anticipated in the natural course of the disease.

In general, abnormal laboratory findings without clinical significance (based on the investigator's judgment) are not to be recorded as AEs. However, abnormal laboratory findings that result in new or worsening clinical sequelae, or that require therapy or adjustment in current therapy, are considered AEs. Where applicable, clinical sequelae (not the laboratory abnormality) are to be recorded as the AE.

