6.9. Prohibitions and Concomitant Therapy

Prohibited medications and products are detailed in [Table 2](#) (Excluded Medications and Treatments).

Generally, the addition of new medications, including nonprescription medications, during the course of the study is discouraged. However, the short-term use of a medication may be authorized by the Investigator. The Investigator must make the decision to authorize the use of any such a medication only after consideration of the clinical situation, the potential for masking symptoms of a more significant underlying event, and whether the use of the medication will

compromise the outcome or validity of the clinical investigation. Other medications may be authorized by the Investigator for conditions other than AD. If medication is required, the name, strength, frequency, duration of use, and reason for use will be recorded in source documents and entered into the CRFs. Medications which have been used chronically by subjects, in particular statins and anti-hypertensives, are allowed for use during the study, except as prohibited in [Table 2](#). No rescue medication for AD is allowed during this study up to Week 4.

Emollients and Moisturizers: Non-medicated emollients or moisturizers will be allowed once daily in a stable regimen as normally used by the subjects. For subjects that apply a non-medicated emollient or moisturizer after an evening shower/bath, the study drug must be applied first to the treatment areas (after the shower/bath). The non-medicated emollient or moisturizer can then be applied but only to other untreated areas of the subject's skin (see [Section 6.10.3](#) for additional details).

Table 2: Excluded Medications and Treatments

Excluded Medications and Treatment	Washout Period Prior to Baseline/Day 1
Biologics such as dupilumab	6 months
Investigational biologics	6 months

 Systemic treatments that could affect AD; e.g. corticosteroids, retinoids, calcineurin inhibitors, hydroxycarbamide (hydroxyurea), methotrexate, cyclosporine, azathioprine, hydroxychloroquine, mycophenolate mofetil, or other immunosuppressive therapies, or systemic treatment with nonsedating antihistamines in a nonstable regimen. Systemic treatments with nonsedating antihistamines (e.g., cetirizine, desloratadine, loratadine) in a stable regimen is allowed. 	4 weeks or 5 half-lives, whichever is longer
PUVA or NBUVB phototherapy	4 weeks
Topical products containing urea	1 week

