7.7.2. Serious Adverse Event

The definitions and reporting requirements of the Food and Drug Administration (FDA)/ICH Guidelines for Clinical Safety Data Management, Definitions and Standards for Expedited Reporting, Topic E2A will be adhered to. Statements regarding mandatory reporting of all serious unexpected adverse drug reactions (SUSARs) to Health Canada [as per C.05.014 (1) of the FDR] will be adhered. If any AEs are serious, as defined by ICH Guidelines for Clinical Safety, required procedures will be followed.

An SAE is defined as any AE that, in the view of either the PI or Sponsor, meets at least 1 of the following serious criteria:

- Fatal
- Life threatening (places the subject at immediate risk of death)
- Requires inpatient hospitalization or prolongation of existing hospitalization
- Results in a persistent or significant incapacity/disability
- Congenital anomaly/birth defect
- Other important medical events that, based upon appropriate medical judgment, may jeopardize the subject and may require medical or surgical intervention to prevent one of the outcomes listed in the above definition

Hospitalization does not include the following:

- Rehabilitation facilities, hospice facilities or respite care (e.g. caregiver relief)
- Nursing homes or skilled nursing facilities
- Emergency room visits
- Same day surgeries (as outpatient/same day/ambulatory procedures)
- <24 hour admissions for observation or evaluation

Hospitalization or prolongation of hospitalization in the absence of a precipitating, clinical AE is not in itself an SAE. Examples include:

- Admission for treatment of a preexisting condition that did not worsen
- Hospitalizations for cosmetic elective surgery, social, and/or convenience admissions
- Pre-planned treatments or surgical procedures should be noted in the baseline documentation for the individual subject

- Diagnostic and therapeutic procedures, such as surgery, should not be reported as AEs; however, the medical condition for which the procedure was performed should be reported if it occurs during the reporting period and meets the definition of an AE. For example, an acute appendicitis that begins during the AE reporting period should be reported as an AE, and the resulting appendectomy should be recorded as treatment of the AE.

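### The atopic dermatitis exemption in Protocol 7.7.1 has no exception for serious worsening, so an inpatient admission for a flare judged anticipated and unequivocally disease-related need not be reported as an AE or SAE

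*Protocol*

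**What the plan says.** Protocol 7.7.1 starts with a general rule: "The definition of AEs includes worsening of a pre-existing medical condition". It then sets a specific exclusion for the study disease. The exclusion covers progression of AD, including new or worsened signs and symptoms of an expected kind, and is limited to those "which are collected as clinical efficacy variables and assessed as unequivocally associated with the disease progression and /or lack of efficacy". For events of this kind, the instruction to sites is that they "should NOT be reported as adverse events unless the disease progression is greater than anticipated in the natural course of the disease".

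Protocol 7.7.2 defines seriousness on top of AE status: "An SAE is defined as any AE that, in the view of either the PI or Sponsor, meets at least 1" of the listed criteria. One criterion is "Requires inpatient hospitalization or prolongation of existing hospitalization". The section later adds: "Hospitalization or prolongation of hospitalization in the absence of a precipitating, clinical AE is not in itself an SAE". Its first example of such an admission is treatment of an existing condition that had not become worse.

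Protocol 7.7.5 applies the 24-hour report to adverse events that meet the serious criteria. SAP 13.1 defines treatment-emergent AEs from recorded AEs and tabulates the serious ones from that set.

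**The concern.** An exemption for expected fluctuation of the study disease is ordinary. It keeps efficacy outcomes from being counted a second time as AEs. The difficulty is that this one depends on whether the worsening was expected and on its attribution, and neither says how serious the event was. Because an SAE must first be an AE, a serious event that the exemption removes at the first step has no way back in.

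At stake is whether an inpatient admission of a child aged 2 to 5 reaches expedited reporting and the safety tables. Safety is part of the primary objective (Protocol 5.1.1). The treatment-emergent SAE table is where a reader would look for a difference between arms in serious events.

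**Working it through.** No arithmetic applies, because the point rests on definitions. The check is to take one case through the text in order: a child is admitted as an inpatient for worsened AD.

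1. **Is it an AE?** The general rule in 7.7.1 says yes, since a pre-existing condition has worsened. The AD sentence then removes it if all of the following hold: the signs or symptoms were anticipated; they are collected as efficacy variables; the investigator judges them unequivocally due to disease progression or lack of efficacy; and the progression is no greater than anticipated in the natural course. If any one fails, the event stays an AE. If all hold, the specific sentence displaces the general rule.
2. **Can it still be an SAE?** 7.7.2 requires an AE as its starting point. The principal investigator or the Sponsor may judge seriousness, but that judgement applies only to something already classed as an AE.
3. **Does the admission bring it back?** Hospitalisation is a criterion applied to an AE. Without a precipitating clinical AE, 7.7.2 says that it is not in itself an SAE.
4. **Does another passage restore it?** The AE footnote to the schedule (Protocol Section 2), 7.1.7 and 7.7.5 set collection periods and reporting duties for AEs and SAEs as already defined. Protocol 7.8 adds no reporting route for disease-related events. SAP 13.1 works from recorded AEs and has no separate table of AD-related admissions.

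The wording that points the other way:

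| Text | Direction | Does it settle the case? |
|---|---|---|
| 7.7.1, worsening of a pre-existing condition | Report | No: the AD sentence is a specific exclusion from it |
| 7.7.2, example of an admission that is not an SAE, limited to a condition that had not worsened | Report, by implication | No: it is an example, and it does not make AD worsening an AE |
| 7.7.1, exception for progression greater than anticipated | Report, if the investigator so judges | No: the expected course is not defined and not tied to seriousness |

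One investigator can call an admitted flare greater than anticipated and report an SAE. Another can call it an unequivocal flare of relapsing disease and report nothing. Each can point to protocol text in support.

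**The case against.** The strongest reply is that the exemption is narrow. It needs an unequivocal attribution to disease, so an ambiguous case stays an AE. Admissions for something that is not an efficacy variable, such as infection, fall outside it. Entry requires mild or moderate disease that has been stable for 4 weeks without significant flares, and unstable AD is excluded (Protocol 6.6.1, 6.6.2). Emergency room visits and admissions under 24 hours do not count as hospitalisation. In such children a true inpatient admission within 4 weeks could readily be judged greater than anticipated. All of this stands, and it makes the gap small. It does not close it, because nothing says that a serious flare counts as greater than anticipated.

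A reader might infer that drug reactions resembling eczema would be lost. The documents do not support that as a general claim. The word unequivocally keeps doubtful cases in, and Protocol 7.1.6 requires application-site reactions to be told apart from existing inflammation. What remains is a confident misattribution.

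A reader might also infer that such a child would escape every safeguard. That goes too far. Protocol 6.7.1 allows treatment to stop for any medical condition posing substantial risk. Protocol 7.8 requires contact with the Medical Monitor for any condition possibly related to study drug. Protocol 6.7.2 provides for consultation with the Sponsor and Medical Monitor where prohibited medication is needed. SAP 7.1 tabulates reasons for study discontinuation by arm. These are other ways for a case to surface, but none is an SAE report.

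**Conclusion.** The gap is real on the text and narrow in practice. A serious AD flare judged anticipated, no greater than the natural course and unequivocally disease-related need not be recorded as an AE or SAE, and would then be absent from expedited reporting and the treatment-emergent SAE table. The conclusion assumes that sites apply 7.7.1 before 7.7.2 and read the AD sentence as overriding the general rule on pre-existing conditions.

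The size cannot be stated as a number. The documents give no rate of serious AD worsening and no indication of how often all the conditions would be met. Any count of missed events, or any confidence bound built on one, would rest on invented inputs. The frequency is probably low. The efficacy analysis is unaffected: vIGA-AD and EASI are scored at visits whatever the AE coding, and SAP 12.1.1 handles discontinuation for an AE and for lack of efficacy in the same way.

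Two stronger readings should be left aside. One is that 7.7.1 breaches the ICH guideline named in 7.7.2; that guideline's text is not in the documents, so a breach cannot be shown from them. The other is that the rule "No rescue medication for AD is allowed during this study up to Week 4" makes such admissions more likely; the documents offer no evidence on this.

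**What to change.** Add one sentence to the AD exemption in Protocol 7.7.1, for example: *This exemption does not apply to worsening of AD that meets any seriousness criterion in Section 7.7.2; such an event is recorded as an AE and an SAE whether or not it was anticipated.* Align the hospitalisation sentence in 7.7.2, so that an admission for worsened AD counts as having a precipitating AE. Protocol 7.7.5 and SAP 13.1 then pick these events up with no change of their own.

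The cost is protocol wording, a site memo and possibly a few extra SAE reports. If enrolment has finished, a query to sites before database lock about inpatient admissions for AD would recover the same information. The change concerns what is reported, not how any child is treated.
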